6. STUDY INTERVENTIONS

In this study, there are no therapeutic study interventions, however the study does involve protocol-required diagnostic or monitoring procedures (study interventions) that are considered to be low risk or burden to the study participant, specifically blood draws.

6.1. Study Intervention(s)

6.1.1. Performance or Administration of Diagnostic or Monitoring Study Interventions

Not applicable.

6.2. Methods to Minimize Bias

To maintain the blinded nature of interventional studies C3391003 and C3391002, all C3391007 study participants and investigators as well as the sponsor will remain blinded to the Cohort assignment of the C3391002 or C3391003 study participant in the same household until C3391003 and C3391002 becomes unblinded. Additionally, the detailed individual results of NAb and ADA to AAV and fordadistrogene movaparvovec vector DNA

will be considered sensitive clinical data and will not be shared with the participants, investigators, or the sponsor until any blinded interventional study that contributes to this study becomes unblinded. Data results from this study of household contacts of DMD patients from the open-label interventional studies C3391008 and C3391001 will not be blinded.

7. PARTICIPANT DISCONTINUATION/WITHDRAWAL FROM STUDY

7.1. Participant Discontinuation/Withdrawal From the Study

A participant may withdraw from the study at any time at his/her own request. Reasons for discontinuation from the study include the following:

- Refused further follow-up;
- Lost to follow-up;
- Death;
- Study terminated by sponsor.

If a participant withdraws from the study, he/she may request destruction of any remaining samples taken and not tested, and the investigator must document any such requests in the site study records and notify the sponsor accordingly.

If the participant withdraws from the study and also withdraws consent for disclosure of future information (see Section 7.1.1), no further evaluations should be performed and no additional data should be collected. The sponsor may retain and continue to use any data collected before such withdrawal of consent.

7.1.1. Withdrawal of Consent

Participants should notify the investigator in writing of the decision to withdraw consent for future follow-up, whenever possible. The withdrawal of consent should be explained in detail in the medical records by the investigator, as to whether the withdrawal was from study procedures and/or study follow-up, and this information should be entered on the appropriate CRF page. In the event that vital status (whether the participant is alive or dead) is being measured, publicly available information should be used to determine vital status only in a manner that is in accordance with local law.

7.2. Lost to Follow-up

A participant will be considered lost to follow-up if he or she repeatedly fails to return for scheduled visits and is unable to be contacted by the study site.

The following actions must be taken if a participant fails to return to the clinic for/attend a protocol-required study visit:

- The site must attempt to contact the participant and reschedule the missed visit as soon as possible and ascertain whether or not the participant wishes to and/or should continue in the study;
- Before a participant is deemed lost to follow-up, the investigator or designee must make every effort to regain contact with the participant (where possible, 3 telephone calls and, if necessary, a certified letter to the participant's last known mailing address or local equivalent methods). These contact attempts should be documented in the participant's medical record;
- Should the participant continue to be unreachable, he/she will be considered to have withdrawn from the study.

8. STUDY ASSESSMENTS AND PROCEDURES

The investigator (or an appropriate delegate at the investigator site) must obtain a signed and dated ICD and assent, as appropriate (Section [10.1.3](#)), before performing any protocol-required procedure, in accordance with the site's remote consenting process and guidelines.

Study procedures will be conducted by the home health care vendor at the participant's home, and/or by the investigator via remote communication. Results of any assessments performed by the home health care vendor will be documented by the home health care vendor personnel, (electronically) transferred to the central site, reviewed by the PI or his/her designee, and transcribed to a CRF by study site personnel.

Protocol-required study procedures and their timing are summarized in the [SoA](#). Protocol waivers or exemptions are not allowed. Adherence to the study design requirements, including those specified in the [SoA](#), is essential and required for study conduct.

Safety issues related to protocol-required procedures should be discussed with the sponsor immediately upon occurrence or awareness to determine whether the participant should continue or discontinue from the study.

All screening evaluations must be completed and reviewed to confirm that potential participants meet all eligibility criteria. The investigator will maintain a screening log to record details of all participants screened and to confirm eligibility or record reasons for screening failure, as applicable.

Every effort should be made to ensure that protocol-required tests and procedures (study interventions) are completed as described. However, it is anticipated that there may be circumstances outside the control of the investigator that may make it infeasible to perform the test. In these cases, the investigator must take all steps necessary to ensure the safety and well-being of the participant. When a protocol-required test cannot be performed, the

investigator will document the reason for the missed test and any corrective and preventive actions that he or she has taken to ensure that required processes are adhered to as soon as possible. The study team must be informed of these incidents in a timely manner.

The total blood sampling volume for individual participants in this study is approximately 18 mL. For participants who weigh <20 kg, the expected blood volume is approximately 8 mL.

For samples being collected and shipped, detailed collection, processing, storage, and shipment instructions and contact information will be provided to the investigator site prior to initiation of the study.

8.1. Efficacy Assessments

Not applicable.

8.2. Safety Assessments

Planned time points and description for all safety assessments (AE collection) are provided in the [SoA](#). Unscheduled clinical laboratory measurements or other safety assessments may be obtained at any time during the study to assess any perceived safety issues.

8.2.1. Weight Measurement

Weight will be measured with a standardized, digital scale placed on a stable, flat surface. Participants must remove shoes, bulky layers of clothing, and jackets so that only light clothing remains. They must also remove the contents of their pockets. Participants should be instructed to step gently onto the scale, place both feet together in the center of the scale and stand straight with eyes directed ahead. Participants should be instructed to stand still and not sway. Measurement will be recorded after the weight has stabilized. Body weight should be reported with precision to one decimal place (eg, 0.1 kg).

8.2.2. Protocol-Required Clinical Safety Laboratory Assessments

Protocol-required clinical safety laboratory assessments will not be performed in this study.

8.2.3. Baseline Characteristics

Demographic information such as year of birth (for the patients of the interventional studies and C3391007 participants), race, ethnicity, gender, and relationship to the interventional study patient will be collected in compliance with local regulations.

At Screening, the average number of hours per week that the participant is in the same room as the interventional study patient will be collected. At Visit 2, the best estimate of number of days of contact (in same room) as the interventional study patient during the first two weeks after administration of IP will be collected.

8.3. Adverse Events and Serious Adverse Events

The definitions of an AE, SAE, and Research Related Injury (RRI) can be found in [Appendix 2](#). The investigator is required to assess whether any AE may be related to participation in the study. All AEs (ie, serious and non-serious, including those attributed to a protocol-required procedure identified as RRI) are collected in the clinical study database.

AEs may arise from symptoms or other complaints reported to the Investigator by the participant (or, when appropriate, by a caregiver, surrogate, or the participant's legally authorized representative) or they may arise from clinical findings of the Investigator or other HCPs (clinical signs, test results, etc.).

The investigator and any qualified designees are responsible for detecting, documenting, and recording events that meet the definition of an AE or SAE and remain responsible to pursue and obtain adequate information both to determine the outcome and to assess whether the event meets the criteria for classification as an SAE or caused the participant to discontinue the study intervention (see [Section 6.1](#)).

During the active collection period for safety events (see Section 8.3.1), each participant or parent/legal guardian/legally authorized representative will be questioned about the occurrence of AEs in a nonleading manner.

In addition, the investigator may be requested by Pfizer Safety to obtain specific follow-up information in an expedited fashion.

8.3.1. Time Period and Frequency for Collecting AE and SAE Information

The time period for actively eliciting and collecting AEs and SAEs (“active collection period”) for each participant begins at the time that the blood collection is performed at Visits 1, 3, and 4, and ends 2 hours after that procedure/intervention has completed.

The investigator is required to perform appropriate follow-up of each adverse event throughout and after the active collection period and until the AE/SAE or its sequelae resolve or stabilize at a level acceptable to the investigator and Pfizer concurs with that assessment.

If the participant withdraws from the study and also withdraws consent for the collection of future information, the active collection period ends when consent is withdrawn.

If a participant definitively discontinues or temporarily discontinues study intervention because of an AE or SAE, the AE or SAE must be recorded on the CRF and the SAE reported using the NIS AE Report form.

Since there is no product under study, there is no post-study active reporting period for the SAEs to be communicated to Pfizer Safety.

8.3.1.1. Reporting SAEs to Pfizer Safety

All SAEs occurring in a participant during the active collection period (see [Section 8.3.1](#)) are reported to Pfizer Safety on the NIS AE Report form immediately upon awareness, as indicated in [Appendix 2](#); under no circumstance should the time between awareness and reporting of the SAE exceed 24 hours. The investigator will also submit any updated SAE data to the sponsor within 24 hours of it being available.

Reportable SAEs include events related to an approved, Pfizer product taken by the participant under routine care, during the time they are participating in the study, should such events come to the attention of the Investigator (including an overdose or a medication error that led to the SAE). Refer to [Appendix 2](#) for the definition of an overdose or medication error.

8.3.1.2. Recording Nonserious AEs and SAEs on the CRF

All applicable SAEs and nonserious AEs, as described in [Appendix 2](#), that are directly observed and/or spontaneously reported by the participant during the active collection period (described in [Section 8.3.1](#)) will be recorded on the AE page of the CRF.

8.3.2. Method of Detecting AEs and SAEs

The method of recording, evaluating, and assessing causality of AEs and SAEs and the procedures for completing and transmitting SAE reports are provided in [Appendix 2](#).

Care will be taken not to introduce bias when detecting AEs and/or SAEs. Open-ended and nonleading verbal questioning of the participant is the preferred method to inquire about AE occurrences.

8.3.3. Follow-up of AEs and SAEs

After the initial AE/SAE report, the investigator is required to proactively follow each participant at subsequent visits/contacts. For each event, the investigator must pursue and obtain adequate information until resolution, stabilization, the event is otherwise explained, or the participant is lost to follow-up (as defined in [Section 7.2](#)).

In general, follow-up information will include a description of the event in sufficient detail to allow for a complete medical assessment of the case and independent determination of possible causality. Any information relevant to the event, such as concomitant medications and illnesses, must be provided. In the case of a participant death, a summary of available autopsy findings must be submitted as soon as possible to Pfizer Safety.

Further information on follow-up procedures is given in [Appendix 2](#).

8.3.4. Regulatory Reporting Requirements for SAEs

Prompt notification by the investigator to the sponsor of an SAE is essential so that legal obligations and ethical responsibilities towards the safety of participants and the safety of a study intervention under clinical investigation are met.

The sponsor has a legal responsibility to notify both the local regulatory authority and other regulatory agencies about the safety of a study intervention under clinical investigation. The sponsor will comply with country-specific regulatory requirements relating to safety reporting to the regulatory authority, IRBs/ECs, and investigators.

8.3.5. Exposure During Pregnancy or Breastfeeding, and Environmental Exposure

The requirements for reporting pregnancy or breastfeeding and environmental exposure apply throughout the entire active collection period and are outlined below; when such reports are required per protocol, the report must be transmitted to Pfizer Safety within 24 hours of investigator awareness.

8.3.5.1. Exposure During Pregnancy

An EDP occurs if:

- A female participant is found to be pregnant while taking any Pfizer product under routine care, at any time during the study period (eg, a concomitant medication that is not required by the study protocol); or,
- A male participant uses any Pfizer product under routine care during the study period (ie, a concomitant medication that is not required by the study protocol) and his partner subsequently becomes pregnant; or,
- A female participant is found to be pregnant and is a household contact of a person who received a Pfizer gene therapy (such as fordadistrogene movaparvovec) within 2 months prior to or during pregnancy.

The investigator must report the EDP to Pfizer Safety within 24 hours of the investigator's awareness, whether or not an SAE has occurred.

- The initial information submitted should include the anticipated delivery date of the baby (see below for information related to termination of pregnancy).
- An EDP report is not required if the Pfizer product taken under routine care is specifically approved for use in pregnant women (eg, vitamins) and is administered in accord with authorized use. However, if the infant experiences an SAE associated with such a drug, the SAE must be reported along with the EDP.
- The Investigator must report the EDP to Pfizer Safety on the NIS AE Report Form and the EDP Supplemental Form. Relevant details of the exposure and the pregnancy

will be collected from the time informed consent was provided until final study follow-up. If there is an SAE associated with the EDP, then the SAE is reported to Pfizer Safety using the NIS AE Report Form.

Follow-up must be conducted to obtain general information on the pregnancy and its outcome for all EDP reports. The investigator will follow the pregnancy until completion (or until pregnancy termination) and notify Pfizer Safety of the outcome as a follow-up to the initial EDP Supplemental Form. For a live birth, information regarding the structural integrity of the neonate at the time of birth should be provided. In the event of a termination, the reason(s) for termination should be provided and information regarding the structural integrity of the terminated fetus should be included in the report (if available; not required if pre-procedure test findings were conclusive for a congenital anomaly and those findings are provided in the report).

Abnormal pregnancy outcomes are considered SAEs. If the outcome of the pregnancy meets the criteria for an SAE (ie, ectopic pregnancy, spontaneous abortion, intrauterine fetal demise, neonatal death, or congenital anomaly), then the investigator should follow the procedures for reporting SAEs.

Additional pregnancy outcomes that must be reported to Pfizer Safety as SAEs include:

- Spontaneous abortion including miscarriage and missed abortion;
- Neonatal deaths that occur within 1 month of birth should be reported, without regard to causality, as SAEs. In addition, infant deaths after 1 month should be reported as SAEs when the investigator assesses the infant death may be related to exposure to the Pfizer product used under routine care during the study.

Additional information regarding the EDP may be requested by the sponsor. Further follow-up of birth outcomes will be handled on a case-by-case basis (eg, follow-up on preterm infants may be requested to identify developmental delays). In the case of paternal exposure, the investigator will provide the participant with the Pregnant Partner Release of Information Form to deliver to his partner. The investigator must document in the source documents that the participant was given the Pregnant Partner Release of Information Form.

8.3.5.2. Exposure During Breastfeeding

- An EDB occurs if female participant is found to be breastfeeding while taking any Pfizer product under routine care, at any time during the study period (eg, a concomitant medication that is not required by the study protocol).
- A female participant is found to be breastfeeding while being a household contact of a person who received a Pfizer gene therapy (such as fordadistrogene movaparvovec).

- An EDB report is not required when a Pfizer product specifically approved for use in breastfeeding women (eg, vitamins) is administered in accord with authorized use. However, if the infant experiences an SAE associated with such a drug, the SAE must be reported along with the EDB.

The investigator must report an EDB to Pfizer Safety within 24 hours of the investigator's awareness, whether or not an SAE has occurred.

- The investigator must report EDB to Pfizer Safety using the NIS AE Report form.
- If the EDB is associated with a SAE, then the SAE must be reported using the same NIS AE Report form.

8.3.5.3. Environmental Exposure

Not applicable. Environmental or occupational exposure is not reportable in this study since there is no Pfizer product under study.

8.3.6. Cardiovascular and Death Events

Not applicable.

8.3.7. Disease-Related Events and/or Disease-Related Outcomes Not Qualifying as AEs or SAEs

Not applicable.

8.3.8. Adverse Events of Special Interest

Not applicable.

8.3.8.1. Lack of Efficacy

In this study, lack of efficacy is reportable to Pfizer Safety for an approved Pfizer product used by the participant under routine care, if the Investigator is made aware.

Lack of efficacy is the failure of expected pharmacologic action or therapeutic benefit. Lack of efficacy should be reported as an SAE to Pfizer Safety if the lack of efficacy involves a vaccine, a contraceptive or a product that is used in the treatment of life-threatening diseases or conditions (eg, anti-infectives) (excluding HIV and cancer).

For Pfizer products that are not covered in paragraph above, lack of efficacy is reportable to Pfizer Safety only if associated with an SAE.

8.3.9. Medical Device Deficiencies

Not applicable.

8.4. Treatment of Overdose

Not applicable.

8.5. Pharmacokinetics

Pharmacokinetic parameters are not evaluated in this study.

8.6. Pharmacodynamics

Pharmacodynamic parameters are not evaluated in this study.

8.7. Genetics

Not applicable.

8.8. Biomarkers

8.8.1. Banked Biospecimens

Biobank specimens will only be drawn in participants who weigh >20 kg.

Banked Biospecimens in this study are:

- 10 mL whole blood Prep B2 sample(s) optimized for serum.
- Banked Biospecimens will be collected as local regulations and IRB/ECs allow.
 - Banked Biospecimens may be used for research related to fordadistrogene movaparvovec and DMD.
- The samples may be analyzed as part of a multistudy assessment of analytes or biomarkers involved in immunity and/or immune response to fordadistrogene movaparvovec or other gene therapies.
- The sponsor will store the Banked Biospecimens in a secure storage space with adequate measures to protect confidentiality. Banked Biospecimens will be labeled with a code. The key between the code and the participant's personally identifying *information* (eg, name, address) will be held at the study site and will not be provided to the sample bank.
- Samples for banking will be stored indefinitely or for another period as per local requirements.
- Details on processes for collection and shipment of these samples can be found in the central laboratory manual.

8.9. Immunogenicity Assessments

8.9.1. Blood Samples for Immunogenicity and Vector DNA Measurement

Blood samples will be collected for analysis of NAb to AAV9 and ADA to AAV9 titers.

Blood samples will also be collected for qPCR analysis of fordadistrogene movaparvovec vector DNA.

Detailed collection, processing, storage, and shipment instructions will be provided in the central laboratory manual.

Samples will be analyzed using validated analytical methods in compliance with Pfizer SOPs.

Lab results will be electronically transferred from the central lab to the Sponsor's database.

8.10. Health Economics

Health economics/medical resource utilization and health economics parameters are not evaluated in this study.

9. STATISTICAL CONSIDERATIONS

9.1. Statistical Hypotheses

There are no hypotheses to be tested.

9.2. Sample Size Determination

Approximately 50 to 250 participants will be enrolled. [Table 1](#) below shows the expected precision, defined as the upper and lower 95% confidence limits, of the estimate of the proportion of participants who are negative for NAb to AAV9 at Baseline and who develop NAb to AAV9 post-Baseline for various numbers of enrolled participants. These calculations assume that 75% of the participants will be seronegative for NAb to AAV9 at Baseline.

Table 1. 95% CI of the Estimate of the Proportion of Participants who are NAb Seronegative to AAV9 at Baseline and who Seroconvert to AAV9 Post-Baseline

Total Enrolled in C3391007	Interventional study patient who received fordadistrogene movaparvovec				Interventional study patient who received placebo			
	N ^a	Number NAb seronegative to AAV9 at Baseline ^b	Percent who seroconvert to AAV9	95%, CI ^c	N ^a	Number NAb seronegative to AAV9 at Baseline ^b	Percent who seroconvert to AAV9	95%, CI ^c
50	33	25	1%	(0, 4.9)	17	13	1%	(0, 6.4)
			5%	(0, 13.5)				
			10%	(0, 21.8)				
			25%	(8.0, 42.0)				
			50%	(30.4, 69.6)				
100	66	50	1%	(0, 3.8)	34	26	1%	(0, 4.8)
			5%	(0, 11.0)				
			10%	(1.7, 18.3)				
			25%	(13.0, 37.0)				
			50%	(36.1, 63.9)				
150	100	75	1%	(0, 3.3)	50	38	1%	(0, 4.2)
			5%	(0.1, 9.9)				
			10%	(3.2, 16.8)				
			25%	(15.2, 34.8)				
			50%	(38.7, 61.3)				
200	133	100	1%	(0, 3.0)	67	50	1%	(0, 3.8)
			5%	(0.7, 9.3)				
			10%	(4.1, 15.9)				
			25%	(16.5, 33.5)				
			50%	(40.2, 59.8)				
250	167	125	1%	(0, 2.7)	83	62	1%	(0, 3.5)
			5%	(1.2, 8.8)				
			10%	(4.7, 15.3)				
			25%	(17.4, 32.6)				
			50%	(41.2, 58.8)				

a. Assumes, on average two thirds of patients are treated with fordadistrogene movaparvovec and one third are treated with placebo across the interventional studies.

b. Assumes 75%, are NAb seronegative at Baseline.

c. Assumes all participants within households and between households are independent.

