4. STUDY DESIGN

4.1. Overall Design

This single center, low-interventional study to include approximately 50 to 250 participants is designed to estimate the likelihood of developing NAbs to AAV9 because of exposure to shed viral vector material released by a DMD patient treated with fordadistrogene movaparvovec in clinical studies. This study will include participants who live or work in the same household as a patient in one of the fordadistrogene movaparvovec interventional studies which may include Study C3391003, C3391002, C3391008, or C3391001. Given the timing and logistics of the interventional studies, some may have no household contacts participating in C3391007. Up to 5 participants from the same household may be enrolled.

Eligible participants will undergo phlebotomy provided by a Home Health Care Vendor at three home visits as specified in the [Schedule of Activities](#). As a control, seroconversion or rise of antibody titer against other AAVs may also be quantified.

The total duration of participation in the study is approximately 4 months, including up to 48 days for the screening/baseline period and 56 ± 10 days of follow-up after the interventional study patient is dosed with investigational product. The screening/baseline period may be extended if there are delays in the interventional studies.

The single center conducting this study is located in the United States.

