9.5. Data Analysis

Detailed methodology for summary and statistical analyses of data collected in this study will be documented in the SAP, which will be dated, filed, and maintained by the sponsor. The SAP may modify the plans outlined in the protocol; any major modifications of primary endpoint definitions or their analyses would be reflected in a protocol amendment.

For the primary, secondary, and each of the exploratory endpoints listed in Section 3, the proportion (and 95% CI) of C3391007 participants will be estimated for 2 groups of participants:

- fordadistrogene movaparvovec: household contacts of patients in interventional studies C3391002, C3391003, C3391001, and C3391008
- placebo: household contacts of patients in interventional studies C3391002 and C3391003

using generalized estimating equations methods with study as covariate to account for correlated responses within the same household. A binomial distribution with a log link and an exchangeable correlation matrix within each household (ie, between any two members of a household the correlation is the same) will be used. Proportions and 95% confidence intervals will be provided separately for each visit (except for Detectable fordadistrogene

movaparvovec vector DNA in participants who seroconvert via either ADAs or NAbs) and overall at any time during the study.

Incidence of AEs will be summarized/listed.

Pharmacogenomic or biomarker data from banked biospecimens will be collected pursuant to local regulations/IRB during or after the trial and retained for future analyses; the results of such analyses are not planned to be included in the CSR.

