1. VERSION HISTORY

This Statistical Analysis Plan (SAP) V3 for study C3391007 is based on the protocol amendment #1 dated 05 Apr 2022.

Table 1. Summary of Changes

Version/ Date	Associated Protocol Amendment	Rationale	Specific Changes
V3/ 17 May 2024	Protocol amendment #1	To clarify that height was not collected according to protocol and age category summary is not needed due to small sample size	Section 3.4 Removed age category groups in demographic characteristics Removed height and BMI measurement in baseline summary
		To update statistical analysis method due to small number of enrolled patients	Section 5.2.2 Removed model based analysis for confidence interval for proportion Sections 6.1, 6.2, 6.3 Removed GEE analysis and 95%CI from the analysis and summary Section 6.4 Removed subgroup analysis
		To clarify the summary results needed for interim analysis	Section 7 Added “In order to minimize possibility of unblinding internal study team, the external vendor will provide only the percent of participants whose family members received fordadistrogene movaparvovec and converted.”

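### Table 1 overstates precision at a 1% seroconversion rate: all ten printed upper limits are lower than zero observed events would give with a two-sided Clopper-Pearson or Wilson interval

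*Protocol*

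**What the plan says.** Protocol 9.2 sets no target width and no single sample size: "Approximately 50 to 250 participants will be enrolled". Table 1 then gives the "expected precision, defined as the upper and lower 95% confidence limits, of the estimate of the proportion" of baseline-seronegative contacts who seroconvert, for totals of 50, 100, 150, 200 and 250.

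The footnotes supply the inputs. Footnote a: on average "two thirds of patients are treated with fordadistrogene movaparvovec and one third are treated with placebo". Footnote b: "Assumes 75%, are NAb seronegative at Baseline". Footnote c: "Assumes all participants within households and between households are independent". The interval method is not named.

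The fordadistrogene movaparvovec side shows rates of 1%, 5%, 10%, 25% and 50%. The placebo side shows 1% only.

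On clustering, Protocol 4.1 says "Up to 5 participants from the same household may be enrolled", and Protocol 9.5 says that for the analysis "an exchangeable correlation matrix within each household (ie, between any two members of a household the correlation is the same) will be used".

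SAP V3 gives as a reason for change "To update statistical analysis method due to small number of enrolled patients" and removes the GEE analysis and the 95% confidence intervals. SAP 5.2.2 now defines only the proportion x/n.

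**The concern.** A Wald interval needs a reasonable number of events. At 1% the table puts a fraction of an event into the formula, and the resulting upper limit can be lower than the limit one would report after seeing no events at all. A precision that zero events could not deliver is not an expected precision.

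The 1% rows are the ones a reader would turn to. The study is meant to tell families how large a possibly low risk is, and 1% is the only rate tabulated for placebo contacts. With 50 enrolled, the table suggests that a 1% rate could be bounded below 5%. Since SAP V3 no longer plans confidence intervals, Table 1 is also the only numerical statement of precision in the two documents. Its error is largest at small enrolment, which is the situation that SAP V3 describes.

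**Working it through.** **Inputs.** From Table 1: 25, 50, 75, 100 and 125 seronegative contacts (fordadistrogene movaparvovec) and 13, 26, 38, 50 and 62 (placebo), rate p = 0.01, two-sided 95%, z = 1.96, independence.

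**Step 1: reproduce the printed limits.** Wald upper limit = p + 1.96·√(p(1−p)/n). For n = 25: 0.01 + 1.96·√(0.0099/25) = 0.01 + 0.039 = 4.9%, as printed. The lower limit is negative and is shown as 0. The same formula reproduces all ten 1% cells and every other fordadistrogene cell to the printed decimal. The arithmetic is therefore sound, and the method is inferred from this exact match.

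**Step 2: expected events.** n × 0.01 runs from 0.25 to 1.25 (fordadistrogene) and from 0.13 to 0.62 (placebo).

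**Step 3: limits with zero events.** Clopper-Pearson: 1 − 0.025^(1/n). Wilson: z²/(n + z²). For n = 25 these are 1 − 0.025^(0.04) = 13.7% and 3.84/28.84 = 13.3%.

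**Step 4: mean upper limit at a true 1%.** Sum over x of the Binomial(n, 0.01) probability times the Clopper-Pearson upper limit at x events.

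| Group | n | Printed upper limit, % | Clopper-Pearson, 0 events | Wilson, 0 events | Mean Clopper-Pearson at true 1% |
|---|---|---|---|---|---|
| Fordadistrogene | 25 | 4.9 | 13.7 | 13.3 | 15.35 |
| | 50 | 3.8 | 7.1 | 7.1 | 8.83 |
| | 75 | 3.3 | 4.8 | 4.9 | 6.53 |
| | 100 | 3.0 | 3.6 | 3.7 | 5.35 |
| | 125 | 2.7 | 2.9 | 3.0 | 4.63 |
| Placebo | 13 | 6.4 | 24.7 | 22.8 | 26.16 |
| | 26 | 4.8 | 13.2 | 12.9 | 14.87 |
| | 38 | 4.2 | 9.3 | 9.2 | 10.94 |
| | 50 | 3.8 | 7.1 | 7.1 | 8.83 |
| | 62 | 3.5 | 5.8 | 5.8 | 7.50 |

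The printed value is the smallest figure in every row. At a true 1%, zero events is the likeliest result for n = 25: 0.99^25 = 78%.

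**Step 5: could the table's own method give 4.9% from data?** No. With 25 people a Wald interval is (0, 0) at zero events. At one event its upper limit is 0.04 + 1.96·√(0.04·0.96/25) = 11.7%.

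**Step 6: other rows.** Printed limit against mean Clopper-Pearson upper limit:
- 5%: 13.5 against 21.4 (n = 25), 11.0 against 14.9 (n = 50), 8.8 against 10.3 (n = 125).
- 25%, n = 25: 42.0 against 45.8.
- 50%, n = 25: 69.6 against 70.1.

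The 5% cell at n = 25 is borderline, since 13.5 lies between the two zero-event limits for that n (13.3 and 13.7). The problem fades as the rate rises.

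**Step 7: scale.** For the zero-event Clopper-Pearson limit to be 4.9% or lower, n must be at least 74. That is 74/(0.75 × 2/3) = 148 enrolled, against 50 in that row. This is the best case (no events), not the size needed for the average case.

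**Step 8: clustering (assumed values).** The documents give no intraclass correlation (ICC) and no household sizes. With m contacts enrolled per household and 75% of them seronegative independently, the design effect is 1 + (m − 1)·0.75·ICC. For m = 1 it is 1.0. For m = 5 and ICC = 0.5 it is 1 + 4·0.75·0.5 = 2.5, and √2.5 = 1.58. Over m = 1 to 5 and ICC = 0 to 0.5, half-widths are 0 to 58% wider.

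**The case against.** The strongest objection is that little depends on the table. No hypothesis is tested, no acceptable upper limit is set, and enrolment is a range that Protocol 4.1 ties to the timing and logistics of the interventional studies. SAP V3 has dropped the confidence intervals, so restating a planning table gives readers of the results no interval. This stands as a limit on importance. It does not make the stated precision correct.

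The effect is also uneven and depends partly on the convention. The gap is about 0.2 to 0.3 percentage points at n = 125 and 0.6 to 0.7 at n = 100. Jeffreys limits at zero events are about equal to the printed value at n = 75 (3.28 against an unrounded 3.25) and lower at n = 100 and 125 (2.5 and 2.0). One-sided 95% Clopper-Pearson limits are also lower at n = 100 and 125 (2.95 and 2.4). These points are right, so the zero-event comparison holds for two-sided Clopper-Pearson and Wilson limits and not for every method. But Table 1 states two-sided limits, and the mean upper limit at a true 1% exceeds the printed value in all ten cells even with Jeffreys (fordadistrogene: 11.4, 6.8, 5.2, 4.4 and 3.9).

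Finally, footnote c discloses the independence assumption, and any ICC is the reviewer's assumption. That is fair. Clustering is secondary here, and the main point does not rest on it.

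**Conclusion.** The concern holds. In all ten 1% cells the printed upper limit is lower than zero events would give with a two-sided Clopper-Pearson or Wilson interval, and lower than the average upper limit at a true 1%. The understatement is large at small n: at n = 25 the zero-event limit is about 2.7 to 2.8 times the printed 4.9%, and at n = 13 about 3.6 to 3.9 times the printed 6.4%. It is minor at n = 125.

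The conclusion rests on the table's own group sizes and independence assumption, and on the inference that the limits are Wald limits, which the exact reproduction supports. It concerns planning and interpretation only, so it should be corrected but does not threaten the analysis. The documents do not give the number actually enrolled, so which row applies is unknown.

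**What to change.** Restate Table 1 with Clopper-Pearson or Wilson limits at whole event counts (0, 1, 2 and so on) for both groups, and name the method. For the 25-contact row, the Clopper-Pearson upper limit would be 13.7% at zero events and 20.4% at one event.

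Add a sensitivity column that applies a design effect over a stated, assumed range of ICC and household size. It should include single-contact households and count only baseline-seronegative members.

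The calculation is one table, with no extra participants and no change to the planned analysis. If the table stays in the protocol, the change is an amendment with the review that Protocol 10.1.1 describes; placing the restated table in the SAP would be lighter. The other cost is that the stated precision at low rates becomes less favourable.
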